8.3. Safety Population

The Safety population is defined as all subjects receiving the allocated treatment after randomization. This population will be used for the analysis of safety endpoints.

9. Description of Efficacy Endpoints and Analyses

The primary analysis of the primary efficacy endpoint will be performed using the ITT population. The sensitivity analysis of the primary endpoint will be performed using the PP population. All secondary efficacy endpoints will be performed using the ITT population. Safety analysis will be based on the safety population.

In efficacy or exploratory analyses, covariate analyses will be conducted to assess the impact of various prognostic factors on closure and to demonstrate the robustness of the primary analysis. Prognostic factors (i.e., covariates) will be included if they are found to be contributing factors (i.e., the individual covariate p-value is less than 0.10). Potential prognostic factors to be considered include:

• Ulcer area

Duration of ulcer

Gender

• HbA1c

•Ulcer Location

Diabetes type

• Race

• Nicotine Use

Baseline BMI

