9.4.7 SAFETY ANALYSES

AEs/SAEs related to the investigational product, study ulcer and/or study procedures and will be recorded.

AEs will be coded according to the most recent version of the Medical Dictionary for Regulatory Activities (MedDRA) AE coding dictionary, and grouped by body system. The number and percentage of subjects experiencing at least one AE of any type, AEs within each body system and AEs within each preferred term will be presented for each treatment group. Separate summaries will be provided for all AEs, device related AEs, SAEs and AEs leading to withdrawal.

All safety parameters will be summarized descriptively by treatment assignment. No inferential statistics are planned.

Listings of complications will be presented, include complication type, relation to study device, relation to procedure, action taken, and clinical outcome. Separate listings will be constructed for complications with possible, probable, or definite relationship to the device, serious complications, and for all complications. The listing for all complications will be sorted by complication type.

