8.1. Intent-to-Treatment Population

The Intent-to-Treat (ITT) population, defined as all randomized subjects who received at least one application of study intervention, will be the primary population for the analysis of primary and secondary efficacy endpoints.

Confidential Page 12 of 23

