10.1. General Statistical Considerations

All study data collected in the eCRF will be presented in subject data listings. Statistical analyses will be performed using SAS® for Windows, version 9.4 or later. Descriptive statistics (e.g., n, mean, standard deviation, median, etc.) will be calculated by treatment group for continuous variables. Frequencies and percentages will be presented by treatment group for categorical variables.

Unless otherwise specified, all testing will be performed using two-sided test at the 0.05 level of significance.

Confidential Page 16 of 23

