10.6. Safety Analysis

Safety will be assessed through reports of adverse events and serious adverse events. Adverse Events related to the device, study ulcer and/or study procedures and all Serious Adverse Events will be recorded.

All safety parameters will be summarized descriptively by treatment. No inferential statistics are planned.

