10.7. Adverse Events

Adverse events will be coded using the MedDRA Medical Dictionary. Treatment Emergent AE's (TEAE) are defined as events with an onset on or after the first randomized treatment. TEAEs will be summarized by treatment group, System Organ Class, and preferred term. The following TEAE summaries will be provided:

- TEAEs by severity grade
- TEAEs by relationship to study treatment.

In addition, separate summaries of serious adverse events, and adverse events resulting in discontinuation of study treatment will be presented.

The safety population will be used for the safety analyses. Summary will be provided by subject and by adverse events. Subjects will be counted only once for subject-based analysis.

Confidential Page 18 of 23

If the same event changes in severity for a subject, the worst severity will be reported. Subjects could be counted more than once for AE-based analysis, all AEs will be reported for AE-based analysis.

An adverse event is considered to be treatment emergent if (1) it was not present when the active phase of the study began, and it is not a chronic condition that is part of the subject's medical history; or (2) it is present at the start of the study or as part of the subject's medical history, but the severity or frequency increased during the active phase. The active phase of the study begins on the day of the first dose of test article and the last dose of test article.

Treatment-emergent adverse events (TEAE) will be summarized for each treatment group by body system and preferred term. The severity of all adverse events will be determined by the investigator's judgment and classified as mild, moderate or severe.

Treatment groups will be compared with respect to the incidence of adverse events (all and TEAEs) and the proportion of subjects withdrawing from the study for adverse events by reason of withdrawal. Comparisons will be made overall, by body system and by preferred term and will be further categorized by severity and by study drug relationship.

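### The SAP's safety population omits treated subjects who never received their allocated product, and no rule assigns events after mixed exposure

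*SAP*

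**What the plan says.** SAP 8.3 defines the set: "The Safety population is defined as all subjects receiving the allocated treatment after randomization". It adds: "This population will be used for the analysis of safety endpoints". SAP 9 repeats the instruction ("Safety analysis will be based on the safety population"), and SAP 10.7 repeats it for adverse events ("The safety population will be used for the safety analyses").

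The ITT population in SAP 8.1 is worded differently. It is "defined as all randomized subjects who received at least one application of study intervention", with no requirement that the intervention be the one allocated.

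On grouping, Protocol 9.4.7 says: "All safety parameters will be summarized descriptively by treatment assignment". SAP 10.6 stops one word earlier: "All safety parameters will be summarized descriptively by treatment". The SAP therefore leaves open whether assigned or received treatment is meant. Protocol 9.3 defines only the ITT and per-protocol populations, so the protocol offers no safety population to fall back on. Neither document contains an as-treated rule.

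Listings are not tied to any population. SAP 10.1 says: "All study data collected in the eCRF will be presented in subject data listings".

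**The concern.** A safety population exists to count everyone who was exposed, under what they were exposed to. Here, membership depends on whether the treatment received matched the allocation. Anyone who was treated but never received the allocated product fails that test, so their events are missing from the incidence tables and from the between-group safety comparisons planned in SAP 10.7 and 11.1.3. The same subject can still contribute to the primary efficacy result.

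The second gap concerns subjects who received their own product at some visits and another product at others. They stay in the population, but nothing says under which product their events are counted. Grouping by assigned arm would credit an event to a product that may not have been on the wound when it occurred.

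The setting gives some opportunity for error. Under Protocol 6.2.1, Apligraf is ordered for each subject before the arm is known, and the sponsor also supplies AMNIOEXCEL Plus, so both allografts can be on site at randomization.

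**Working it through.** The plan gives no figure on this point to reproduce. The check is to apply the definitions to each kind of subject, and then to illustrate the size.

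**Step 1. Apply the wording.** SAP 8.1 gives the ITT column, SAP 8.3 the safety column, and Protocol 9.4.7 with SAP 10.6 the last column.

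| Subject | ITT | Safety population | Where events are tabulated |
|---|---|---|---|
| Received only the allocated treatment | In | In | Assigned arm, same as received |
| Allocated one allograft, only ever received the other | In | Out | Nowhere; listings only |
| Allocated an allograft, received SOC alone after randomization (SOC is Intervention 1 in the protocol synopsis) | In | Out | Nowhere; listings only |
| Received the allocated allograft at some visits and the other at some visits | In | In | Assigned arm under the protocol; unstated in the SAP |
| Allocated SOC, given an allograft over SOC dressings | In | Arguably in, since SOC was received | Assigned arm under the protocol; unstated in the SAP |

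The exclusion falls on rows 2 and 3. Rows 4 and 5 are a problem of attribution.

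**Step 2. Illustrate the size.** The documents give neither a misallocation rate nor an adverse event rate, so both are assumed. Inputs: 38 subjects exposed to a product (the planned arm size, SAP 5), of whom k were exposed to it by error and never received their own product; 2 events among the 38 - k correctly allocated; and an event in each of the k. Intervals are exact Clopper-Pearson 95%, the SAP 11.1.1 method for a single proportion.

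- All exposed subjects counted: (2 + k)/38
- SAP 8.3 wording: 2/(38 - k)

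| k | All exposed counted | SAP 8.3 wording | Gap (points, unrounded rates) |
|---|---|---|---|
| 0 | 2/38 = 5.3% (0.6 to 17.7) | 2/38 = 5.3% (0.6 to 17.7) | 0 |
| 1 | 3/38 = 7.9% (1.7 to 21.4) | 2/37 = 5.4% (0.7 to 18.2) | 2.5 |
| 2 | 4/38 = 10.5% (2.9 to 24.8) | 2/36 = 5.6% (0.7 to 18.7) | 5.0 |
| 3 | 5/38 = 13.2% (4.4 to 28.1) | 2/35 = 5.7% (0.7 to 19.2) | 7.4 |

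At the other extreme, if none of the k subjects has an event, the true figure is 2/38 = 5.3%. The SAP wording then gives 2/37 = 5.4% to 2/35 = 5.7%, an overstatement of 0.1 to 0.5 points. If the only event on a product occurs in one wrongly exposed subject, the table shows 0/37 where the exposed rate is 1/38 = 2.6%.

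**The case against.** The strongest reply is that the affected group is very small. Allografts are applied weekly while the ulcer is open (Protocol 6.1.1.1), and SAP 8.3 asks that the allocated treatment be received, not that nothing else be received. A single-visit error, the likelier kind, leaves the subject in. Both allograft arms also include SOC, so a SOC subject given an allograft has arguably still received the allocated treatment. Several safeguards work against a sustained swap: the EDC system names the cohort, product and lot number are recorded (Protocol 8.2), and source data are fully verified (Protocol 10.1.6). All of this stands, and it limits the exclusion to subjects who never received their allocated product.

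A reader might infer that anyone ever given the wrong product drops out of every safety output. The documents do not support that. Mixed-exposure subjects remain in the population, SAP 10.1 lists all eCRF data without restriction, Protocol 9.4.7 plans separate complication listings, and the Medical Monitor reviews study-related SAEs (Protocol 10.1.5). The loss is from summary tables and comparisons, not from the record.

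It may also be said that the drafters simply meant subjects treated after randomization. That is possible, but the word allocated is in the definition, and a programmer would have to code it. The narrow scope lowers the likely impact; it does not make the rule correct for the subjects it reaches.

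**Conclusion.** The point holds in limited form. Followed as written, SAP 8.3 removes from the safety summaries and comparisons any randomized subject who was treated but never received the allocated product, while SAP 8.1 keeps that subject for efficacy. For subjects exposed to more than one product, the gap is the absence of an attribution rule, together with the protocol's grouping by assigned arm.

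The likely effect is small. With no such subject, nothing changes. The shifts of 2.5 to 7.4 points rest on one to three wholly misallocated subjects who each have an event, and both conditions are assumptions. Even then the intervals overlap widely. It would be wrong to infer that a mix-up took place or that events were concealed: the documents report none. The definition should be corrected because it gives the wrong answer in exactly the case a safety population should handle, and the correction is cheap.

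**What to change.** 1. In SAP 8.3, define the safety population as all randomized subjects who received at least one application of any study treatment (AMNIOEXCEL Plus, Apligraf or SOC) after randomization, summarized by treatment actually received. Keep the restriction to after randomization, because every subject has SOC dressings during screening.
2. Add a rule for exposure to more than one product. For example, count a subject exposed to an allograft not assigned to them under that allograft, or show such subjects separately. State that SOC given alongside an allograft is not mixed exposure.
3. Reconcile the grouping in Protocol 9.4.7 and SAP 10.6 with this rule, so that both documents name the same basis.
4. Record the revision as a documented SAP change with its reason. SAP 12 shows that some study data had already been evaluated, and SAP 6 provides for no analytical blinding, so the timing should be transparent.

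The cost is a few sentences and no new data, since product and lot number are already collected. The one small downside is that safety groups may differ slightly from the randomized groups; a footnote giving the numbers moved would cover it.

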9.1. Primary Endpoint Analysis

The primary endpoint of this study is the incidence of complete wound closure, as assessed by the Investigator at or before Week 12 of the Treatment Phase and confirmed closed 2 weeks later. Confirmed complete wound closure is defined as complete skin re-epithelialization that is without drainage or dressing requirements two weeks later.

Confidential Page 13 of 23

A subject is considered to have a closed wound (i.e., a closure success) if the subject's treated wound closes between week 1 and 12 and is noted by the site as closed on both follow-up visits.

A subject is considered to not have a closed wound (i.e., a closure failure) if they meet any of the following:

- the subject's treated wound does not close by week 12
- the subject's treated wound closes between week 1 and 12 and is noted as open on either or both of the follow-up visits.

A subject is considered to have an undetermined wound closure if the subject's treated wound closes between week 1 and 12 and the subject misses either or both of the follow-up visits. These subjects may become part of extended analyses.

The primary analysis will be conducted on the ITT population. The proportion of subjects with confirmed closed study wound, as assessed by the investigator, will be compared between AMNIOEXCEL Plus and Apligraf, and AMNIOEXCEL Plus and SOC. The proportion of subjects with confirmed complete wound closure will be compared using the Cochran–Mantel–Haenszel (CMH) test and logistic regression.

For the primary efficacy analysis, missing values will be imputed using last observation carried forward (LOCF). The differences in confirmed complete wound closure rate between treatment arms will be summarized along with 95% confidence intervals.

A point estimate of the incidence will be presented along with its associated exact 95% confidence interval based on the binomial distribution for Active Treatment and Control Treatment patients respectively.

The complete wound closure as assessed by the Investigator at the end of the Treatment Phase will be listed for each patient.

In addition, subgroup analyses of the primary endpoint will be performed for age, sex, race, region, and other groupings if appropriate.

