8.2. Per Protocol Population

The Per Protocol (PP) population, defined as all subjects in the ITT population for whom there were no major protocol violation, will be used as supportive for the analyses of the primary and secondary endpoints.

For the per protocol analysis, no data points will be imputed, all missing values will remain as missing.

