9.5. Missing Data

For primary efficacy evaluation of data points, the last available observation (LOCF) will be used. In the analyses of using the planimetry data, the last available planimetric value will be used for a discontinued subject. All subjects discontinued during the treatment period and before 100% wound closure during the treatment phase of the study will not be replaced and will be considered treatment failures for evaluating the primary and secondary endpoints.

10. Description of Other Variables and Analyses

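### The plan does not say whether LOCF turns a closed wound with a missed confirmation visit into a primary success, or whether that subject stays in the denominator

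*SAP*

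**What the plan says.** SAP 9.1 sorts subjects into three outcomes.

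- Success: the wound "closes between week 1 and 12 and is noted by the site as closed on both follow-up visits".
- Failure: the wound does not close by Week 12, or it closes and is then "noted as open on either or both of the follow-up visits".
- Undetermined: the wound closes by Week 12 and the subject "misses either or both of the follow-up visits. These subjects may become part of extended analyses".

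For the primary analysis, the same section adds: "For the primary efficacy analysis, missing values will be imputed using last observation carried forward (LOCF". SAP 9.5 repeats it: "For primary efficacy evaluation of data points, the last available observation (LOCF) will be used". Protocol 9.1 and 9.4.5 carry the same classes and the same LOCF rule.

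Three other provisions bear on the point.

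- The ITT population is "defined as all randomized subjects who received at least one application of study intervention", so undetermined subjects belong to it.
- SAP 9.5 has a failure rule, but it reaches only part of the missing data: "All subjects discontinued during the treatment period and before 100% wound closure during the treatment phase of the study will not be replaced", and these subjects count as treatment failures.
- SAP 8.2 switches imputation off, but only for the supportive analysis: "For the per protocol analysis, no data points will be imputed, all missing values will remain as missing".

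**The concern.** The group at issue is narrow: closed by Week 12, at least one confirmation visit missed, and no open reading at any follow-up visit attended. The classification leaves these subjects neither success nor failure. The LOCF rule, which has no exception, makes them successes. No passage says which rule prevails, or whether a subject who is not a success stays in the denominator.

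Confirmation two weeks later is part of the primary endpoint. Literal LOCF would supply that confirmation in just the subjects for whom a required reading is absent. Each arm's closure rate depends on the reading chosen, and the between-arm difference depends on it when the arms have unequal numbers of such subjects. The trial is open label and SAP 6 provides no blinding at analysis, so an unwritten rule could be settled with results by arm in view.

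**Working it through.** **Where LOCF can change a primary outcome**

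| Last information on the wound | SAP 9.1 class or SAP 9.5 rule | Literal LOCF |
|---|---|---|
| Discontinued before closure | failure | failure |
| Never closed by Week 12 | failure | failure |
| Closed, then seen open at an attended follow-up visit | failure | failure |
| Closed, a confirmation visit missed, never seen open | undetermined | success |

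Only the last row differs. If LOCF stops short of these subjects, the primary imputation rule does essentially nothing. If it reaches them, the undetermined class has no role in the primary analysis. The two provisions cannot both have effect.

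The class definitions also overlap. A subject who misses follow-up visit 1 and is open at visit 2 meets both the failure and the undetermined definitions. Whichever primary rule is adopted should rank them.

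**Inputs**

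- From the documents: 38 per arm (SAP 5), two-sided 0.05 (SAP 10.1), CMH test (SAP 9.1), and the Z-based interval with continuity correction for a difference (SAP 11.1.1).
- Assumed: the confirmed counts, the number undetermined and their split between arms, and a single stratum for CMH, because no strata are named.

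The plan gives no figure for this group. Its only precision figure, a 13.5% half-width, reproduces as an uncorrected interval for a difference: 1.96 × √(2 × 0.9 × 0.1 / 38) = 13.49 points.

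**Formulas**

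- Effect of one subject on an arm: 1/38 = 2.63 points.
- 95% CI for a difference: (p1 − p2) ± [1.96 × √(p1(1 − p1)/n1 + p2(1 − p2)/n2) + 0.5 × (1/n1 + 1/n2)].
- CMH, one stratum: (a − E)²/V, where E = n1·m/N, V = n1·n2·m(N − m)/[N²(N − 1)], a is the successes in the first arm, m is all successes and N = n1 + n2.

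**Case 1: confirmed 20/38 v 15/38, four undetermined in total**

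Counted as non-success, every split gives 20/38 − 15/38 = 13.2 points. The SE is 11.33 points, so the half-width is 1.96 × 11.33 + 2.63 = 24.85, the CI is −11.7 to 38.0 and p = 0.25.

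| Undetermined, first arm–second arm | Literal LOCF | Difference (95% CI), p | Excluded | Difference, p |
|---|---|---|---|---|
| 4–0 | 24/38 v 15/38 | 23.7 (−0.8 to 48.2), 0.04 | 20/34 v 15/38 | 19.3, 0.10 |
| 3–1 | 23/38 v 16/38 | 18.4 (−6.3 to 43.1), 0.11 | 20/35 v 15/37 | 16.6, 0.16 |
| 2–2 | 22/38 v 17/38 | 13.2 (−11.7 to 38.1), 0.25 | 20/36 v 15/36 | 13.9, 0.24 |
| 1–3 | 21/38 v 18/38 | 7.9 (−17.1 to 32.9), 0.49 | 20/37 v 15/35 | 11.2, 0.35 |
| 0–4 | 20/38 v 19/38 | 2.6 (−22.5 to 27.7), 0.82 | 20/38 v 15/34 | 8.5, 0.47 |

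**Case 2: near the 90% planning rate with no difference**

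Take 34/38 closed by Week 12 in each arm, with four of the first arm's 34 undetermined and none in the second.

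- Literal LOCF: 34/38 v 34/38 = 0.0 points.
- Excluded: 30/34 v 34/38 = −1.2 points, p = 0.87.
- Non-success: 30/38 v 34/38 = −10.5 points (CI −29.4 to 8.3), p = 0.21.

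The non-success rule can therefore also move the comparison when missed visits are unequal.

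**The case against.** The strongest reply is that the text already leans one way. SAP 9.1 requires the site to have recorded closure at both follow-up visits, and an imputed visit is not recorded by anyone. These subjects have a named third outcome and are referred to extended analyses, and a specific provision normally overrides a general one. This has weight, but it is inference. The contrast with the per-protocol rule, which alone switches imputation off, points the other way. Even if LOCF is ruled out, the denominator question stays open.

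A second reply concerns size. The 4–0 and 0–4 splits are extremes: if each of four subjects is equally likely to fall in either arm, each has probability 1/16, and the three mixed splits cover 14/16 = 87.5%, with LOCF differences of 7.9 to 18.4 points. Missed confirmation visits can arise only in a two-week window, so they should be a small part of the 20% attrition. The SAP's own interval has a half-width of about 25 points in Case 1, and no interval computed here excludes zero. All of this stands, and it limits the consequence without supplying the rule.

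Third, the per-protocol analysis without imputation and the by-subject listings would let a reader find these subjects. That is partial protection: the per-protocol set also drops major violators, so it does not isolate this question.

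**Conclusion.** The concern holds. The documents contain two rules that give different primary outcomes for the same subjects, and neither precedence nor the denominator is stated. Applied literally, the written LOCF rule conflicts with the endpoint's own definition of success.

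The size is 2.6 points on an arm's rate per undetermined subject, between counting that subject as success and as non-success. The effect on the difference depends on imbalance between arms and is nil under LOCF when the split is even. In the examples p falls below 0.05 only at the 4–0 split in Case 1, where the SAP's interval still includes zero. Because the SAP says the study is not adequately powered for hypothesis testing, the consequence lies in the reported rates and differences. If no subject is undetermined, nothing changes. This should be fixed, but it does not undermine the design.

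**What to change.** State in SAP 9.1 and 9.5, and align Protocol 9.4.5, that:

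1. LOCF does not apply to the confirmation visits.
2. Primary success requires closure at or before Week 12 and a recorded closed reading at both follow-up visits.
3. Any open follow-up reading is a failure, and this takes precedence over undetermined.
4. Every other ITT subject, including the undetermined, is a non-success and stays in the denominator.
5. The number undetermined is reported by arm, with two ITT sensitivity analyses: undetermined counted as success, and undetermined excluded.

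The non-success rule follows the plan's own success definition, but Case 2 shows that it penalises an arm with more missed visits. Both sensitivity analyses are needed for that reason.

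The cost is a few sentences and one small table, using data already collected. An arm's reported rate will be 2.6 points lower per undetermined subject than under literal LOCF. Because SAP section 12 (Change from Planned Analysis) shows that the photograph-review data had already been evaluated when it was written, the rule should be recorded as a dated change, noting what outcome data had been seen by then.
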